5.1.2.2 Dose Specifications

The prescription isodose should encompass 95% of PTV. The dose to multiple PTVs within the same patient may vary. If there are multiple PTVs, each should be planned for one of the prescription doses listed above, with each specific covering isodose planned to encompass 95% of each PTV, with normalization to the PTV receiving the highest dose. The highest allowable doses to the target volumes that maintain normal tissue constraints should be used. A goal is that 100% of the CTV is encompassed by the prescription dose. The unit of dose is Gy.

5.1.2.3 Dose Prescription

Is based on the volume of normal tissues irradiated (correlated with mean liver dose), as well as proximity of stomach, duodenum, small and large bowel (GI luminal structures) to the target volumes, as normal tissue constraints must be maintained in this study.

In the absence of adjacent GI luminal structures that may limit dose, the PTV dose prescription should be as high as possible based on mean liver dose (MLD, defined as the mean dose to the liver minus all GTVs), with 6 potential dose levels. Note, no variations in mean liver dose are permitted.

Table 2: SBRT Dose Prescription

Priority Constraint	Prescription Dose	
Allowed MLD (Gy)*	Planned Prescription Dose (Gy)	If the max allowed MLD is exceeded at this planned dose
13.0	50	Reduce to 45 Gy and re-evaluate
15.0	45	Reduce to 40 Gy and re-evaluate
15.0	40	Reduce to 35 Gy and re-evaluate
15.5	35	Reduce to 30 Gy and re-evaluate
16.0	30	Reduce to 27.5 Gy and re-evaluate
17.0	27.5	Ineligible

*< 15.0 Gy for the first 10 patients, regardless of prescription dose

- Vascular tumor thrombosis (e.g., portal vein thrombosis) dose should be treated to the same dose as the parenchymal HCC. However, lower doses are acceptable if required to maintain normal tissue limits, since the cancer density may be lower than parenchymal HCC. Non-tumor bland thrombosis is strongly recommended to NOT be irradiated, to reduce the overall volume irradiated.
- Maximum dose within PTV = 150%. If multiple PTVs exist, 150% of the maximal PTV prescription dose is permitted for all PTVs. Concomitant boost to the GTV to 1-2 dose levels above the prescription dose are recommended, and it is desirable to have a hot spot of at least 40 Gy in the GTV if possible.

- Maximum dose outside PTV = 120% of the maximal PTV prescription.
- Efforts should be made to keep the prescription dose and the 30Gy isodose as conformal as possible.
- Different isodoses may cover different PTVs. If multiple PTVs, the MLD should be evaluated with the prescription dose corresponding to the highest dose level that any PTV is treated. Queries should be directed to the study PI.

5.1.2.4 Technical Factors

Megavoltage equipment with photons of at least 6MV, capable of daily image guidance, with a multileaf collimator for intensity modulation is required. Inverse-planned IMRT, forward planned IMRT and volumetric modulated arc therapy (VMAT) are to be used for planning. CT based planning is required, with a minimum of 5 beam angles. Image guided radiation therapy (IGRT) is mandatory. Breathing motion management is recommended if breathing motion is > 5 mm. Breathing motion assessed on 4DCT and adequately treated with PTV margins < 20 mm is permitted.

5.1.2.5 Localization, Simulation and Immobilization

Custom immobilization is recommended (e.g. With vacuum immobilization, patient positioning boards, knee cushions, and/or breath hold immobilization with active breathing control).

Treatment planning CT scans will be required to define GTV. Multi-phasic IV contrast is recommended for the planning CT (arterial phase and/or delayed phase imaging recommended for GTV delineation, and venous phase for portal vein thrombosis delineation).

Exhale breath hold CT or average phase CT (from 4D CT) may be used as the baseline CT for radiation therapy planning. CT scans obtained during free breathing may not be used for planning. CT scans used for target delineation are recommended to be multi-phase IV contrast scans obtained in exhale breath hold. Exhale breath hold is preferred as it most often is closer to the average position than inhale breath hold, and exhale is more reproducible than inhale. If IV contrast scans cannot be obtained at the time of radiation planning, IV contrast CT scans from diagnostic radiology may be fused to the primary planning dataset to aid in target definition. If contraindications to IV CT contrast exist, IC contrast multiphase MR can be used to help define GTV. Diagnostic MR imaging can be imported to the planning system to aid in target delineation.

All scans used for target delineation should be fused to each other so that the livers are registered to each other for target delineation. Registration will be performed with the best fit liver-to-liver image registration, focusing on the region of the PTVs if deformation or rotation occurs between scans.

Breathing motion assessment. Measurement of target/liver breathing motion is required, unless breath hold is to be used for liver immobilization. Motion may be assessed using 4D CT, fluoroscopy and/or cine MR.

4D CT: A 4D, or respiratory sorted, CT may be obtained for assessing motion if breath hold is not used for liver immobilization.

All patients will have image guidance at the time of each radiation fraction. Cone beam CT is the preferred image guidance.

5.1.2.6 Treatment Planning/Target Volumes

The **Gross Tumor Volume (GTV)** is defined as all suitable parenchymal and vascular HCC visualized on contrast enhanced CT and/or MRI, most often best seen on arterial phase (as hyperintensity) and/or venous or delayed phase (as hypointensity relative to liver). GTVp1 should represent the ‘primary parenchymal (=p) dominant (=1)’ GTV, upon which primary QA will be based. Subsequent lesions can be labeled as GTVp2, GTVp3, GTVp4 and GTVp5). If ‘p’ is not included following “GTV”, the lesion will be assumed to be parenchymal. Vascular HCC thrombi (GTVv) most often are best seen on venous phase imaging as hypointensity relative to the contrast in the vessel. Vascular HCC may be combined with parenchymal HCC (labeled as GTVp or GTVpv) if they are to be treated to the same dose.

Non-tumor thrombi should not be considered as GTV; they should be excluded from contouring. The prescription dose should be annotated to each GTV after the final plan is complete (e.g. GTVp1_50 for a 50Gy target).

For each GTVp, the **Clinical Target Volume (CTV)** is defined as the GTV (CTVp1...CTVp5), with no expansion. The minimal CTVv is the GTVv, with no expansion. **It is expected that there will be no expansion from GTV to CTV for the majority of cases.** However, CTV expansions to include regions at high risk for microscopic disease, including non-tumor vascular (v) thrombi (CTVv), prior TACE (t) sites (CTVt), or adjacent RFA (r) (or other ablation) sites (CTVr) are permitted if judged to be at high risk of recurrence. Such CTVs may be treated to a microscopic dose (27.5 Gy) or up to as high as the prescription dose, at the investigator’s discretion. Separate CTVs should be labeled CTVp1, CTVv2, CTVv3, CTVt4...etc. The prescription dose should be annotated to each CTV after the final plan is complete (e.g. CTVp1_50 for a 50Gy target, and CTVt2_27.5 for a CTV treated to 27.5 Gy).

The **Planning Target Volume (PTV)** will provide a margin around each CTV to compensate for set-up and internal organ motion. PTV nomenclature should follow CTV nomenclature guidelines. For example, PTVv for the PTV around the CTVv and PTVp1 and PTVp2 for PTVs around CTVp1 and CTVp2. A minimum PTV margin of 4 mm around each CTV is required in all directions (for example if active breathing control is used with excellent reproducibility). The maximum permitted PTV margin is 20 mm, expected to be used uncommonly. **PTV margins ≤ 10 mm are a goal.** Asymmetric PTV margins are permitted. The actual PTV used will depend on motion management used, the patients’ motion and reproducibility. **PTVs should not be manually modified due to proximity of adjacent organs at risk (OARs).** The final PTVs should have dose annotated once the plan is final, e.g. PTVp1_50 and PTVv1_27.50 for targets treated to 50 Gy and 27.5Gy, respectively.

Standard target and organ at risk nomenclature will be used.

Heterogeneity Corrections: All dose distributions shall include corrections for tissue heterogeneities. Arterial vascular contrast from the planning dataset is recommended to be converted to water equivalent

density if used for planning. Planning datasets without intravenous contrast may be used for planning.

Planning target volumes around luminal GI tissues are encouraged so that the steepest dose gradients of doses higher than the maximal allowable luminal GI doses are outside the PRV. PRV magnitude will be individualized based on an estimate of expected change day-to-day (5 mm to 30 mm).

Goals of planning are to maximize dose to the target volumes, while maintaining all normal tissue constraints (as defined below). **Reducing the maximal dose and lower dose ‘bath’ to all luminal gastrointestinal normal tissues should be a planning priority to reduce the risk of gastrointestinal toxicity.** Conformality of the prescription dose and the 30 Gy isodose are other goals.

Critical Structures Maximal Doses

Dose values in this section should be read as physical dose in 5 fractions. Note these doses have been modestly reduced from our present standard, with the goal of reducing the risk of toxicity.

Esophagus max (to 0.5 cc):	30 Gy
Stomach max (to 0.5 cc):	29 Gy
Duodenum max (to 0.5 cc):	29 Gy
Small bowel max (to 0.5 cc):	29 Gy
Large bowel max (to 0.5 cc):	30 Gy
Cord + 5 mm max (0.5cc):	25 Gy
Kidneys: Bilateral mean dose	< 10 Gy

-OR-

If there is one kidney mean dose > 10Gy, remaining (or only) kidney V10Gy < 10%

The following organ dose constraints are strongly advised to be met, but are not mandatory:

Stomach (to 5 cc):	< 25 Gy
Duodenum (to 5 cc):	< 25 Gy
Small bowel (to 5 cc):	< 25 Gy
Liver minus all GTVs:	>700cc and D800cc ≤ 18 Gy
Heart max (30cc):	< 30 Gy
Skin (external) max (0.5 cc):	< 32 Gy
Chest wall max (0.5 cc):	< 50 Gy
Gallbladder max (0.5 cc):	< 55 Gy
Common bile duct max (0.5 cc)	< 50 Gy*

*Even though the bile duct is not often well visualized, it is always within the portal region and may be within high dose volumes for central targets, so efforts to reduce hot spots in this region are warranted.

Peer review of all SBRT plans is required prior to starting SBRT (either one-on-one or at GI or SBRT quality assurance rounds) by another radiation oncologist.

Treatment Interruptions

Treatment interruptions should be clearly documented in the patient’s treatment record. Total treatment time is recommended to be 10 days, with allowable total duration between 5 days and 15 days.

Total Treatment Duration

Per protocol: All treatment falls within 15 calendar days

Variation Acceptable: All treatments fall within 16 to 21 calendar days

Deviation Unacceptable: All treatments that take 22 or more calendar days to complete

PTV Dosimetry

Target coverage for each PTV should be considered on its own. If there are multiple tumors, the primary (dominant) PTV should be labeled #1. **The intent is for prescription dose to cover 95% of each PTV.**

If PTVs are not treated as per guidelines, this is a deviation unacceptable. The PTV should be treated to as high a dose as possible, respecting normal tissue constraints, as a dose response has been observed. Modifying required PTVs due to close proximity of adjacent OARs is not permitted.

The following **Table 3** describes variations and deviations in the prescription dose (dose covering 95% of the PTV). **Treating “per protocol” should always be the planning intent.**

Table 3: Variations and Deviations in Prescription Dose

Dose to 95% PTV	PTVs around GTVs*	PTVs around non-GTV CTVs*
Per protocol	Prescription dose +/- 5%	Prescription dose +/- 5%
Variation acceptable	90-95% or 105-110% of prescription dose, and ≥ 25 Gy	90-95% or 105-110% of prescription dose, and ≥ 25 Gy
Deviation unacceptable	<90% or >110% of prescription dose, or < 25 Gy	<90% or >110% of prescription dose, or < 25 Gy
Overall plan deviation unacceptable	< 25 Gy	

*Note that lower doses than the dose-allocation schedule are acceptable if they are required due to adjacent luminal GI structures that may limit the deliverable dose.

Compliance for Critical Structures (organs at risk, OARs)

If non-hepatic OARs limit the prescription dose, the highest dose (from the 6 prescription doses listed in **Table 2** above) should be used, while maintaining OAR dose constraints.

Table 4: Variations and Deviations due to Organs at Risk

Non-liver OARs	Per protocol	Variation acceptable	Deviation unacceptable
Esophagus max (to 0.5 cc):	30 Gy	> 30 but ≤ 34 Gy	> 34 Gy
Stomach max (to 0.5 cc):	29 Gy	> 29 but ≤ 32 Gy	> 32 Gy
Duodenum max (to 0.5 cc):	29 Gy	> 29 but ≤ 32 Gy	> 32 Gy
Small bowel max (to 0.5 cc):	30 Gy	> 30 but ≤ 32 Gy	> 32 Gy
Large bowel max (to 0.5 cc):	30 Gy	> 30 but ≤ 34 Gy	> 34 Gy
SpinalCord_05 + 5 mm max (0.5cc):	25 Gy	> 25 but ≤ 28 Gy	> 28 Gy
Kidneys: Bilateral mean dose	≤ 10 Gy	> 10 but ≤ 12 Gy	> 12 Gy

Table 5: Acceptable & Unacceptable Dose Deviations

Prescription Dose	Liver (minus GTV) mean dose	
	Per protocol (acceptable)	Deviation (unacceptable)
50 Gy	≤ 13 Gy	> 13 Gy
45 Gy	≤ 15 Gy	> 15 Gy
40 Gy	≤ 15 Gy	> 15 Gy
35 Gy	≤ 15.5 Gy	> 15.5 Gy

30 Gy	\leq 16 Gy	$>$ 16 Gy
27.5 Gy	\leq 17 Gy	$>$ 17 Gy

5.2 General Concomitant Medication and Supportive Care Guidelines

Initiation of Proton Pump Inhibitors (PPIs) prior to starting SBRT should be considered for subjects whose treatment plan will contain significant volumes of stomach or duodenum. In these patients, non-steroidal anti-inflammatory drugs should be avoided where possible.

Subjects are prohibited from receiving the following therapies during the Screening and Treatment Phase (including retreatment for post-complete response relapse) of this trial:

- Antineoplastic systemic chemotherapy or biological therapy
- Immunotherapy not specified in this protocol
- Chemotherapy not specified in this protocol
- Investigational agents other than pembrolizumab
- Radiation therapy not specified in this protocol for the treatment of HCC. See Section 5.3.2 for details on radiotherapy for oligoprogressive disease
- Live vaccines within 30 days prior to the first dose of trial treatment and while participating in the trial. Examples of live vaccines include, but are not limited to, the following: measles, mumps, rubella, varicella/zoster, yellow fever, rabies, BCG, and typhoid vaccine.
- Systemic glucocorticoids for any purpose other than the following:
 - To modulate symptoms from an event of clinical interest of suspected immunologic etiology
 - Physiologic doses of prednisone 10 mg (or equivalent) per day
 - Inhaled steroids for management of asthma
 - Use of prophylactic corticosteroids to avoid allergic reactions (e.g., IV contrast day)
 - Topical steroids for management of skin reactions

Subjects who, in the assessment by the investigator, require the use of any of the aforementioned treatments for clinical management should be removed from the trial. Subjects may receive other medications that the investigator deems to be medically necessary.

The Exclusion Criteria describe other medications which are prohibited in this trial.

Any other medication which is considered necessary for the subject's welfare, and which is not expected to interfere with the evaluation of the study drug, may be given at the discretion of the Investigator.

5.3 Duration of Therapy

In the absence of treatment delay / discontinuation due to adverse event(s), treatment may continue until one of the following criteria applies:

- Confirmed disease progression by iRECIST, as defined by Section 11.1.4
- Clinical evidence of disease progression, in the opinion of the Investigator, such that

continuing treatment would not be beneficial for the study subject. Note that further SBRT may be considered for oligoprogressive disease as per Section 5.3.2, and re-challenge with pembrolizumab may be considered in circumstances listed in Section 5.3.1.

- Women who become pregnant or are breastfeeding
- Sexually active subjects who refuse to use medically accepted forms of barrier contraception (e.g. male condom, female condom) during the study
- Termination of the protocol by a regulatory agency or Sponsor, or study medication can no longer be provided
- Significant non-compliance with the protocol schedule in the opinion of the investigator
- Subjects requiring a delay in treatment beyond the allowed timeframe
- Intercurrent illness that prevents further administration of treatment
- Unacceptable adverse event as defined in Section 7
- Subject decides to withdraw from the study
- General or specific changes in the subject's condition which render the subject unacceptable for further treatment in the judgment of the investigator
- Necessity for treatment with another anti-cancer treatment prohibited by this protocol
- Completed 24 months of uninterrupted treatment with pembrolizumab or 35 administrations of study medication, whichever is later.

Note: 24 months of study medication is calculated from the date of first dose.

5.3.1 Retreatment with Pembrolizumab

Subjects who stop pembrolizumab with SD/iSD or better may be eligible for up to one year of additional pembrolizumab therapy if they progress after stopping study treatment. This retreatment is termed the Second Course Phase of this study and is only available if the study remains open (accrual may be completed, but patients still in follow-up) and the subject meets the following conditions:

Either

- Stopped initial treatment with pembrolizumab after attaining an investigator-determined confirmed CR/iCR according to RECIST 1.1/iRECIST, and
 - Was treated for at least 24 weeks with pembrolizumab before discontinuing therapy
 - Received at least two treatments with pembrolizumab beyond the date when the initial CR/iCR was declared

OR

- Had SD/iSD, PR/iPR or CR/iCR and stopped pembrolizumab treatment after 24 months of study therapy for reasons other than disease progression or intolerance

AND

- Experienced an investigator-determined confirmed radiographic disease progression after stopping their initial treatment with pembrolizumab

- Did not receive any anti-cancer treatment since the last dose of pembrolizumab, except for SBRT to oligopressive lesion (see Section 5.3.2)
- Has ECOG performance status of 0 or 1
- Demonstrates adequate organ function as listed in Inclusion Criteria (Section 3.1)
- Female subjects of childbearing potential should have a negative serum or urine pregnancy test within 72 hours prior to receiving retreatment with study medication.
- Female subjects of childbearing potential should be willing to use 2 methods of birth control or be surgically sterile, or abstain from heterosexual activity for the course of the study through 120 days after the last dose of study medication. Subjects of child bearing potential are those who have not been surgically sterilized or have been free from menses for > 1 year.
- Male subjects should agree to use an adequate method of contraception starting with the first dose of study therapy through 120 days after the last dose of study therapy.
- Does not have a history or current evidence of any condition, therapy, or laboratory abnormality that might interfere with the subject's participation for the full duration of the trial or is not in the best interest of the subject to participate, in the opinion of the treating investigator.

Subjects who restart treatment will be retreated at the same dose and dose interval as when they last received pembrolizumab. Treatment will be administered for up to one additional year.

5.3.2 SBRT to Oligopressive lesions

It has been observed that patients with overall stable or responding disease may develop a small number of new or progressive tumor deposits during active treatment. Such patients are likely to benefit from continuing on study treatment, and may be eligible for additional SBRT to these lesions if the following criteria apply:

- Excepting the oligopressive lesions, the best overall response is SD/iSD, PR/iPR or CR/iCR by RECIST 1.1/iRECIST
- The oligopressive lesions has been noted at the second or later CT assessment of disease
- 5 or fewer progressive or new lesions are noted
- The patient has evidence of ongoing clinical benefit – no deterioration in clinical or laboratory parameters suggestive of overall worsening of disease or clinical condition
- The oligopressive lesions are amenable to SBRT – not within previous SBRT field, and SBRT can be delivered with an acceptable safety profile in the opinion of the Investigator. This includes extrahepatic HCC and selected intrahepatic HCC (if the estimates cumulative dose to the liver is within specified dose limits)

Patients with oligopressive lesions that fit the above criteria may be eligible for further SBRT, and should be discussed with the Principal Investigator/Sponsor.

5.4 Duration of Follow Up

Subjects removed from therapy for reasons other than progressive disease/iCPD will be followed at intervals of 90 days (± 14 days) for disease status until progression or initiation of alternative therapy. Follow-up visits can occur remotely via telephone, Ontario Telemedicine Network (OTN), or other appropriate virtual communication if it is in patient's best interest, at the discretion of the Investigator. Subjects who withdraw for refusal will no longer be followed. All subjects will be followed for survival every 90 days (± 14 days) for survival status until death via telephone, in-person visit, or via medical records.

Table 6: Follow-up Guideline

Reason Subjects Removed from study	Follow-Up Period			
	Off Treatment Visit: 4 weeks ± 7 days from the End of Study Drug Administration	Progression Follow-Up: every 3 months ± 14 days after the Off Treatment Visit *	Adverse Event Follow-Up: until resolution or stabilization of adverse event(s)	Survival Follow-Up: every 3 months ± 14 days after the Off Treatment Visit
Objective Disease Progression	X		X	X
Clinical Progression/ Symptomatic Deterioration	X	X	X	X
Adverse Events or clinically significant lab value	X	X	X (weekly FU for 4-weeks, then monthly)	X
All other subjects	X	X	X	X

* Confirmed disease progression (iCPD) is defined according to iRECIST.

** See section 7.6 for Adverse Event Follow-Up details

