10. STUDY CALENDAR

Baseline (pre-study) evaluations are to be conducted within 14 days prior to start of protocol therapy, unless specified differently in the study calendar. Scans (including tumor measurements) x-rays, informed consent, tumor biopsy, and hepatitis testing must be done \leq 28 days prior to the start of therapy. In the event that the subject's condition is deteriorating, laboratory evaluations should be repeated within 48 hours prior to initiation of the next cycle of therapy. Some visits might be conducted remotely and / or some assessments might be deferred as per physician discretion. Some of the safety lab assessments may also be done at external or community laboratories as applicable. In such cases, sites should provide Normal reference ranges of such lab and lab licenses to the Central Office.

The following schedule of assessments applies to all subjects. More frequent assessments should be obtained if clinically indicated. If pre-study laboratory and clinical assessments were done within 5 days prior to treatment initiation, they do not need to be repeated for cycle 1 day 1. For subsequent cycles 2+, day 1 assessments can be completed up to 4 days prior to day 1. A cycle is 21 days long for the purposes of this protocol.

		Cycle 1				Cycle 2	Cycle 3	Cycle 4	Cycle 5	Cycle 6+	Off Treatment Visit ^c	Survival Follow-Up ^c
		Pre-Study	Day 1	Day 2	Day 5	Day 10	Day 1	Day 1	Day 1	Day 1		
Pembrolizumab		A					A	A	A	A		
SBRT			B-----B									
Informed consent (Main and Optional)	X											
Demographics	X											
Medical history	X											
TNM Staging, BCLC Staging	X											
Vascular Thrombosis Staging ^f	X											
Concurrent meds	X	X-----X										
Physical exam	X	X		X ^e		X	X	X	X	X		
Vital signs ^d	X	X	X	X ^e		X	X	X	X	X		
Height	X											
Weight	X	X				X	X	X	X	X		
Performance status	X	X	X			X	X	X	X	X		
Child-Pugh Score	X	X		X ^e		X	X	X	X	X		
ALBI Score	X	X		X		X	X	X	X	X		
CBC w/diff, PT/INR	X	X		X ^e		X	X	X	X	X		
Neutrophil-Lymphocyte Ratio	X	X		X		X	X	X	X	X		
Serum chemistry ^a	X	X		X ^e		X	X	X	X	X		
T3 and TSH	X	X					X		X			
Hepatitis B Testing ^g	X											
Hepatitis C Testing ^h	X											

Anti-HDV Testing ^j	X										
ECHO	X										
EKG	X										
Adverse event evaluation				X-----			X		X		
Tumor measurements	X				X ^m					X ⁱ	
					Documentation (radiologic) must be provided for subjects removed from treatment for progressive disease.						
Radiologic evaluation	X					X ^m				X ⁱ	
B-HCG	X ^b										

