AFP	X	X			X	X	X	X	X	X	
Biopsy for correlative studies	X										
Optional biopsy for correlative studies					X ^k						
Blood for ctDNA/methylation ^l		X		X				X		X	
Blood for cytokine analysis ^l		X		X	X	X		X		X	
Survival status											X

All assessments may be performed up to 2 working days prior to scheduled day.

A: Pembrolizumab 200 mg IV Q3W
 B: SBRT as per Section 5.1.2, commencing Cycle 1 Day 2, consisting of 5 fractions over 5-15 days
 a: Albumin, alkaline phosphatase, total bilirubin, bicarbonate, calcium, chloride, creatinine, glucose, LDH, phosphorus, potassium, total protein, AST, ALT, sodium.
 b: Serum pregnancy test (women of childbearing potential).
 c: See Section 5.4 for post-treatment follow-up requirements.
 d: Blood pressure, temperature, pulse, O₂ saturation, and respiratory rate.
 e: Day of assessment while on SBRT may vary due to weekends, but should be as close to day 3 as possible.
 f: See Appendix 4 for vascular thrombosis staging chart.
 g: All patients should have baseline Hepatitis B screening which should include: HbsAg, Anti-Hbs and Anti-Hbc (total+IgM). For patients with known hepatitis B, or if they have been deemed infected through baseline screening, additional test should include: HBV viral load (DNA), HbeAg and Anti-Hbe. If HBV viral load has been performed within previous 3 months a repeat test is not required. If Hepatitis B Testing has been performed for eligibility less than 28 days prior to start of therapy it is not required to be repeated again as a part of Baseline (Pre-study) evaluations.
 h: All patients should have baseline Hepatitis C screening which should include: Anti-HCV. For patients with known hepatitis C, or if they have been deemed infected through baseline screening, HCV viral load (RNA) should be performed. If HCV viral load has been performed within previous 3 months a repeat test is not required. If Hepatitis C Testing has been performed for eligibility less than 28 days prior to start of therapy it is not required to be repeated again as a part of Baseline (Pre-study) evaluations.
 i: Patients who come off study treatment for reasons other than radiological progression are to have tumor measurements and disease response evaluated every 3mo ± 14 days until documented progression per iRECIST or start of new therapy.

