 j: Only required if the patient has a known history of Hepatitis B and the testing has not been completed previously. If testing has been done previously, a repeat test is not required. If Anti-HDV Testing is required, this must be done ≤ 28 days prior to the start of therapy.
 k: Optional biopsy to be done between 3-6 weeks on study for patients that have consented to procedure
 l: Research bloods to be drawn prior to Pembrolizumab administration. Research blood must be collected on-site at Princess Margaret Cancer Centre.
 m: Radiologic evaluation and tumor measurements should be performed at 12 weeks on treatment and then repeated every 10 weeks thereafter (± 2 weeks). CT scans should be performed at planned time points regardless of any dose delays.

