11. MEASUREMENT OF EFFECT

11.1 Antitumor Effect – Solid Tumors

For the purposes of this study, subjects should be re-evaluated for response every 12 weeks. In addition to a baseline scan, confirmatory scans should also be obtained 4-8 weeks following initial documentation of objective response.

Note, response in the irradiated volume is challenging to assess before 3 months post radiation therapy due to radiation change in the surrounding liver. Even at 3 months, changes in the surrounding liver around the HCC may represent radiation treatment change, rather than tumor progression. Thus, review of images by experienced radiologists is required, as is importance of relaying radiation information to the radiologists, to avoid inaccurate labeling of progression when liver changes are due to radiation effect on the liver.

Response and progression will be evaluated in this study using both RECIST 1.1 and the new criteria proposed by immune modified Response Evaluation Criteria in Solid Tumors (iRECIST) guideline (Seymor 2017). Changes in the largest diameter (uni-dimensional measurement) of the tumor lesions and the shortest diameter in the case of malignant lymph nodes are used in the iRECIST criteria. Overall response will be assessed, as well as response in lesions outside the SBRT treatment field. These criteria keep the uni-dimensional measurement of RECIST, but incorporate the concept of unconfirmed progression (iUPD) noted with the use of immunotherapy. In the case of new lesions, assessments continue as per RECIST 1.1 but are recorded in a separate case report form. Contrasting to RECIST 1.1 new lesions may result in iUPD but immune confirmed progression (iCPD) is only assigned on the basis of this category if at next assessment additional new lesions appear or an increase in size of new lesions is seen (≥ 5 mm for sum of new lesion target or any increase in new lesion non-target); the appearance of new lesions when none have previously been recorded, can also confirm iCPD. iUPD may occur before iPR, iCR or iSD, in contrast to RECIST 1.1 where progression could not occur. Notable in this study, radiated lesions will be counted as part of the response criteria, an exception to the rules of RECIST 1.1.

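### Tumour assessment after stopping treatment runs on a different clock from the on-treatment scans, and subjects whose last dose is at week 0 or 3 have no planned scan near week 12

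*Combined protocol and SAP*

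**What the plan says.** Four places govern when tumours are assessed, and they do not share a clock.

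- **Section 5.4, Table 6.** The first visit is "Off Treatment Visit: 4 weeks ± 7 days from the End of Study Drug Administration". Disease assessment then follows as "Progression Follow-Up: every 3 months ± 14 days after the Off Treatment Visit". The row for subjects stopping because of adverse events is marked for this follow-up.
- **Section 5.4, text.** Subjects taken off therapy for reasons other than progression "will be followed at intervals of 90 days (± 14 days) for disease status until progression or initiation of alternative therapy". No start point is given for the 90 days.
- **Section 10, Study Calendar.** Note m: "Radiologic evaluation and tumor measurements should be performed at 12 weeks on treatment and then repeated every 10 weeks thereafter", with a window of ± 2 weeks. It holds scans to their planned dates through dose delays and is silent on discontinuation. Note i, for subjects stopping for reasons other than radiological progression, asks for "tumor measurements and disease response evaluated every 3mo ± 14 days until documented progression per iRECIST or start of new therapy", again without a start point. The rows for tumour measurement and radiology carry the note i mark in what reads as the Off Treatment Visit column.
- **Section 11.1.** "subjects should be re-evaluated for response every 12 weeks", with no limit to time on treatment. It adds that response in the irradiated volume is hard to assess before 3 months after radiotherapy.

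**The concern.** PFS (Section 13.4) is dated by scans, so a progression date depends on when the subject is next imaged. While treatment continues, that is fixed by time since start. Once treatment stops for a reason other than progression, Table 6 restarts the count from a visit that depends on the last dose. The scan dates then depend on how long the subject tolerated treatment. In a single-arm trial of a combination for which Section 5.1.2.1 anticipates overlapping liver toxicity, early stopping is not a remote event.

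The group at risk is small and specific: subjects who stop for good after one or two doses. They may be imaged once, early, when the irradiated liver is hard to read, and then not again until well past week 12. Because note i and the Section 5.4 text give no start point, a site also cannot tell which schedule applies.

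**Working it through.** The plan gives no figure for this delay, so there is none to reproduce.

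**Step 1. Visit dates.** Inputs: 21-day cycles (Section 10), so doses before week 12 fall at weeks 0, 3, 6 and 9; Off Treatment Visit at 4 ± 1 weeks and follow-up at 3 months ± 2 weeks (Table 6); 90 days = 90/7 = 12.9 weeks (Section 5.4).

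First Table 6 assessment = last dose + 4 + 12.9 weeks. The windows add up to ± 3 weeks.

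| Last dose | Off Treatment Visit (window) | First Table 6 assessment (window) | Weeks after week 12 |
|---|---|---|---|
| week 0 | 4 (3-5) | 16.9 (13.9-19.9) | 4.9 |
| week 3 | 7 (6-8) | 19.9 (16.9-22.9) | 7.9 |
| week 6 | 10 (9-11) | 22.9 (19.9-25.9) | 10.9 |
| week 9 | 13 (12-14) | 25.9 (22.9-28.9) | 13.9 |

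**Step 2. Two readings of the calendar.**

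- *With a scan at the Off Treatment Visit*, last doses at weeks 6 and 9 give nominal scans at weeks 10 and 13, inside week 12 ± 2 (weeks 10-14). Last doses at weeks 0 and 3 give scans at weeks 4 and 7, then 16.9 and 19.9, with nothing planned between.
- *Without one*, all four groups are first imaged 4.9 to 13.9 weeks after week 12.

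**Step 3. Share of progressions caught in the gap (with an Off Treatment scan).** Assumption: exponential PFS, S(t) = 0.5^(t/m), median 3-4 months. That figure is Section 2.2.2's for SBRT alone and is used only to show a range. With 4.345 weeks per month, m = 13.0 or 17.4 weeks.

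- Last dose week 0, gap from week 4 to 12: S(4) − S(12) = 0.8084 − 0.5283 = 0.280 (m = 13.0); 0.8525 − 0.6197 = 0.233 (m = 17.4). So 23-28%, dated at 16.9 instead of 12, about 5 weeks later.
- Last dose week 3, gap from week 7 to 12, among subjects progression-free at week 3: S(4) − S(9) = 0.8084 − 0.6197 = 0.189; 0.8525 − 0.6984 = 0.154. So 15-19%, dated at 19.9 instead of 12, about 8 weeks later.

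**Step 4. Mean delay over all progressions after the last dose.** For each interval between scan dates, multiply its probability by (date on the off-treatment schedule − date on the 12, 22, 32... calendar), and sum. Medians of 3-4 months, follow-up every 90 days or every 13 weeks:

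| Last dose | With Off Treatment scan | Without |
|---|---|---|
| week 0 | 0.2-0.6 weeks | 2.4-2.7 weeks |
| week 3 | 1.0-1.2 weeks | 3.0-3.5 weeks |
| week 6 | 1.4-1.5 weeks | 3.3-3.9 weeks |
| week 9 | 1.3-1.4 weeks | 3.2-3.9 weeks |

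The small means for weeks 0 and 3 with a scan are partly a balance of opposite shifts. In both groups, 1 − S(4) = 15-19% of progressions occur before the early scan and are dated 8 (week 0) or 5 (week 3) weeks earlier than on the calendar. A mean near zero therefore does not show that the dates agree.

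**The case against.** The strongest answer is that the calendar already provides a tumour evaluation at the Off Treatment Visit, so Table 6 does not set the first assessment. That largely stands. The column placement is read from a converted PDF, but both scan rows carry the mark there and survival status sits alone in the last column. On that reading, subjects last dosed at weeks 6 and 9 are covered.

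It also stands that many toxicities lead first to a hold. Section 6.1 allows up to 12 weeks from the last dose before discontinuation, and note m keeps scans on their dates through delays, so those subjects remain due the week-12 scan. Section 10 further allows more frequent assessments when clinically indicated. The calculation assumes none.

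Three stronger readings are tempting, and the documents do not support them.

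- A reader might infer that everyone who stops early for toxicity misses week 12 and is dated 5-14 weeks late. That range holds only for progression arising by week 12, and only if there is no Off Treatment scan.
- A reader might infer that responses are dated late and duration of response is lengthened. Sections 11.1.4 and 13.1 count best response only on treatment, so a response first seen after stopping may not count at all. A later first-response date would in any case shorten duration of response.
- A reader might infer that early stoppers drop out of the response analysis. Section 13.6.2 counts missing data as non-response. Its conflict with the evaluability and replacement rules in Sections 11.1.1 and 13.3 is a separate question.

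What the objection does not remove is the gap for last doses at weeks 0 and 3, or the missing start point in note i and the Section 5.4 text.

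**Conclusion.** The point holds as an inconsistency with a limited but real consequence. Table 6, the calendar notes and Section 11.1 do not agree on what post-treatment assessments are counted from, and none of them keeps week 12 after discontinuation. On the reading most favourable to the plan, subjects last dosed at week 0 or 3 have no planned scan between about week 4 or 7 and about week 17 or 20. Only at the early extreme of both windows does a week-0 stopper reach week 13.9.

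Under the assumed exponential PFS, 23-28% or 15-19% of their later progressions are dated about 5 or 8 weeks after the calendar date. Over all four stopping times the mean shift is 0.2-1.5 weeks with an Off Treatment scan and 2.4-3.9 weeks without. These figures rest on a median borrowed from SBRT alone, nominal visit dates, and no extra or confirmatory scans. The share of early stoppers is not stated, so no bias in the trial's median PFS is claimed.

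**What to change.** Reconcile Section 5.4 (text and Table 6), calendar notes i and m, and Section 11.1:

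1. Count tumour assessments from first dose for every subject without progression, whether or not treatment continues.
2. State that a subject who stops before week 12 for another reason still has the week-12 (± 2) scan. It replaces a routine Off Treatment scan that would fall before week 10.
3. State whether the Off Treatment Visit otherwise includes a scan, and give the start point of the 3-month interval. Later scans may stay 3-monthly.

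Off Treatment Visits and survival contacts need not change. The cost is protocol wording. If the early Off Treatment scan is kept as well, the downside is at most about one extra CT in a few subjects. In return, the first PFS assessment no longer depends on why treatment stopped.
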